## Patients excluded from the study:

If a patient, after being included, is subsequently rejected from participating, any data related to her will be removed from the clinical trial.

The reason for exclusion will be recorded for further analysis.

## Standardization of the Procedure

To ensure the homogeneity and reproducibility of the procedures performed in the study, a detailed protocol has been established for the performance of diagnostic hysteroscopies. This protocol ensures that each intervention is performed under the same conditions, minimizing variations that may influence the results and the evaluation of the pain perceived by the patients.

## 1. Equipment Used

- Ultrasound with transvaginal probe: To evaluate the patient's anatomy before the test and detect possible post-procedure complications.
- Hysteroscope: A 5 mm 30° Betochi diagnostic hysteroscope will be used. If the return pod applies, it must be specified.
- Distension medium: 0.9% saline solution will be used to ensure adequate visualization during the intervention.
- Irrigation pressure: It will be maintained between 100-120 mmHg to ensure correct distension of the uterine cavity without compromising patient safety.

## 2. Hysteroscopy

The procedure will be carried out following a series of standardized steps to ensure its effectiveness and safety.

As a previous step, **in the control group**, the speculum will be placed to assess the vagina and cervix and the vagina and cervix will be irrigated with a syringe, using 0.9% saline solution, up to 4 times, in the same way as if we applied the local anaesthetic.

## **Step 1: Application of Local Anesthesia (if applicable)**

Objective: This protocol aims to ensure the correct and standardized administration of 3% Mepivacaine for local anesthesia of the uterosacral ligaments in patients undergoing outpatient hysteroscopy, with the aim of evaluating its effect on pain management during the procedure.

**1. Drug to be used:** 3% mepivacaine (4 vials of 3 ml each).

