#### Procedure variables

- **Physician who performs the test** (Type of variable: Nominal qualitative) The professional who carries out the procedure.
- **Degree of experience of the physician** (Type of variable: Ordinal qualitative):
  - o Low: 5-20 procedures performed.
  - o Normal: 20-50 procedures performed.
  - o Discharge: >50 procedures performed.
- **Test Duration** (Variable Type: Continuous Quantitative) The total time of the procedure, which could correlate with the pain experienced.
- Use of the outer sheath (return) (Dichotomous qualitative: Yes/No)
- **Bipolar energy use** (Variable type: Qualitative dichotomous) Yes/No. The use of bipolar energy could influence pain due to the impact on the tissues.
- Number of polyps removed (Variable Type: Discrete Quantitative) 1, 2 or
- >2. The number of polyps could affect the level of pain due to time and additional manipulation.
- Number of biopsies taken (Variable Type: Discrete Quantitative) 1, 2 or
- >2. More biopsies may increase discomfort during and after the procedure.
- **Type of endometrial pattern** (Type of variable: Nominal qualitative) Atrophy, proliferative, menstrual or secretory. Different endometrial patterns can influence pain perception.
- **Number of Cavity Entries** (Variable Type: Discrete Quantitative) The number of times the hysteroscope needs to be inserted into the uterine cavity may be influence in the pain.
- **Insertion technique** (Variable type: Nominal qualitative) Direct entry vs. with speculum and forceps. Insertion techniques could have different implications on perceived pain.

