#### 2. Equipment Needed

• 4 vials of 1.7 ml 3% Mepivacaine.

- Carpule needle (length: 25 mm, gauge: 27).
- Toiletries (sterile gloves, antiseptic, sterile gauze).
- Basic monitoring (pulse oximeter for vital signs control if necessary).

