#### 3.2. Anesthesia Injection

- The uterosacral ligaments are identified through the posterior region of the cervix, on both sides. 2 vials (3.4 ml) of 3% Mepivacaine will be injected into each uterosacral ligament, using a 25 mm Carpule needle.
- The needle should be inserted approximately 2-3 mm deep at each injection site.
- Infiltration should be carried out slowly, to avoid rapid dispersion of the anesthetic and to ensure its appropriate local action.

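### The drug line for mepivacaine gives 4 vials of 3 ml (12 ml), but the equipment list and the injection step both give 6.8 ml; the 3 ml figure is the outlier and most likely wrong

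*Protocol*

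**What the plan says.** Three places in the protocol, all within Step 1 of Standardization of the Procedure, state the quantity of mepivacaine:

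- Item 1, Drug to be used: "3% mepivacaine (4 vials of 3 ml each".
- Item 2, Equipment Needed: "4 vials of 1.7 ml 3% Mepivacaine".
- Item 3.2, Anesthesia Injection: "2 vials (3.4 ml) of 3% Mepivacaine will be injected into each uterosacral ligament". The same item makes clear that there are two injection sites: "The uterosacral ligaments are identified through the posterior region of the cervix, on both sides".

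Step 1 opens by giving its purpose as the "correct and standardized administration of 3% Mepivacaine for local anesthesia of the uterosacral ligaments".

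**The concern.** The first statement gives a different vial size from the other two. Mepivacaine is the only study drug, and the line in question is the one that defines it, in a section whose purpose is to make every administration the same. A reader who orders or prepares the drug from that line would work with 3 ml vials. A reader who works from the next two items would use 1.7 ml vials.

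What is at stake is uniform delivery of the intervention. The injection step gives its amount both as a vial count and as a volume. The two agree only if a vial holds 1.7 ml. With 3 ml vials they conflict, and an operator who counted vials would give more drug than one who measured millilitres. The variables listed under Patient variables, Procedure variables and Variables of post-procedure pain do not include the volume injected, so on the listed variables such a difference would not be visible at analysis.

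**Working it through.** **Inputs**

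- Concentration: 3% in all three places. By unit conversion, 3% = 30 mg/ml.
- Drug to be used: 4 vials, 3 ml each.
- Equipment Needed: 4 vials, 1.7 ml each.
- Anesthesia Injection: 2 vials, stated as 3.4 ml, per ligament; 2 ligaments.

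**Formulas**

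Total volume = vials × ml per vial, or ligaments × ml per ligament. Dose in mg = volume × 30.

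**The plan's own injection figure**

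2 vials × 1.7 ml = 3.4 ml. This reproduces the volume printed in the injection step with the vial size from the equipment list. Read the other way, 3.4 ml / 2 vials = 1.7 ml per vial.

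**The three statements side by side**

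| Place in Step 1 | Total volume | Total dose | Per ligament |
|---|---|---|---|
| Drug to be used | 4 × 3 = 12 ml | 12 × 30 = 360 mg | 6 ml, 180 mg (equal split) |
| Equipment Needed | 4 × 1.7 = 6.8 ml | 6.8 × 30 = 204 mg | 3.4 ml, 102 mg (equal split) |
| Anesthesia Injection | 2 × 3.4 = 6.8 ml | 6.8 × 30 = 204 mg | 3.4 ml, 102 mg (volume as printed) |

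The 12 ml and 6.8 ml totals are products of the printed figures; the protocol prints neither.

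**Can the injection step be carried out with 3 ml vials?**

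- By volume: 3.4 / 3 = 1.13 vials per ligament, or 6.8 / 3 = 2.27 of the four vials. The step says two vials per ligament, and no section describes using part of a vial.
- By vial count: 2 × 3 = 6 ml per ligament. The step says 3.4 ml.

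It fails on either reading, so 3 ml cannot be reconciled with the injection step.

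**Size of the discrepancy**

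- Per patient: 12 − 6.8 = 5.2 ml; 5.2 × 30 = 156 mg; 12 / 6.8 = 1.76, i.e. 76% more.
- Per ligament: 6 − 3.4 = 2.6 ml; 2.6 × 30 = 78 mg.
- If 3 ml vials were stocked but the operator measured 3.4 ml per ligament, the excess would be zero.

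**The case against.** The strongest reply is that the dose is already settled. The injection step is the only instruction on what to inject, and it states the volume in millilitres. The equipment list, from which one would naturally stock, agrees with it. On this view the 3 ml is one stray numeral that the next two items override. The 76% excess would need two departures from the protocol: stocking 3 ml vials against the equipment list, and ignoring the printed 3.4 ml. Nothing in the document suggests that 3 ml vials are in use. It also gives no maximum dose, so no safety consequence of 360 mg can be shown from it. All of this stands. It limits the weight of the point and makes 76% a worst case, but it does not remove the contradiction.

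Other possible explanations do not help the 3 ml figure:

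- Item 3.3, Post-Injection Monitoring, allows the anaesthetic to be given again for persistent severe pain. So 6.8 ml is the initial dose and not necessarily all that a patient receives. But the drug line still counts four vials; what differs is the volume per vial.
- The control-group irrigation is done "up to 4 times, in the same way as if we applied the local anaesthetic". This fits with four applications, but it sets a ceiling on irrigations and says nothing about vial volume, so it supports neither side.

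The data-capture remark also needs a limit. The predefined Excel sheet is not reproduced in the protocol and could hold a volume field that the variable lists omit.

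**Conclusion.** The contradiction is real and stands in the current protocol text. Two of the three statements, including the operative one, give 1.7 ml per vial and 6.8 ml (204 mg) for the four vials. The drug line implies 12 ml (360 mg), and its 3 ml is the outlier. It is most likely a slip, although the protocol does not say outright which figure is intended.

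The practical effect ranges from zero, if operators follow the stated millilitres, to 5.2 ml (156 mg, 76%) above the intended initial dose, if 3 ml vials are supplied and two whole vials are injected into each ligament. The milligram figures rest only on 3% meaning 30 mg/ml. The upper end assumes both departures described above.

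The sample size calculation does not use the dose and is unaffected, as is the planned comparison. The point should be corrected because it is a conflicting quantity for the only study drug, in the section that is supposed to standardize its administration.

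**What to change.** After the sponsor confirms the vial size stocked, change item 1 of Step 1 to read: 3% mepivacaine, 4 vials of 1.7 ml each (6.8 ml, 204 mg in total; 3.4 ml, 102 mg per ligament). It would help to label this the initial dose, given the repeat administration allowed in item 3.3. If 1.7 ml is confirmed, Equipment Needed and Anesthesia Injection already agree and need no change.

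The cost is one corrected number plus a short clarification. Recording the volume injected (ml) among the procedure variables is an optional extra field that would let the team verify uniform dosing; the correction does not depend on it.

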#### 2. Equipment Needed

• 4 vials of 1.7 ml 3% Mepivacaine.

- Carpule needle (length: 25 mm, gauge: 27).
- Toiletries (sterile gloves, antiseptic, sterile gauze).
- Basic monitoring (pulse oximeter for vital signs control if necessary).

#### 3. Application technique

#### 3.1. Patient Preparation

- Gynecological position: The patient should be placed in a gynecological position (dorsal lithotomy) on the examination table.
- Vaginal and perineal hygiene: Antisepsis is not required due to the minimal risk of infection at the site of the anesthetic puncture
- Clinical evaluation: A rapid review of the patient's general condition will be carried out to confirm the suitability of local anesthesia.

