## **Summary of the Consent Delivery Procedure:**

- 1. Delivery and signature of the informed consent at the time of indication of the hysteroscopy.
- **2.** Explanation of the study and requirement of your signature for inclusion in the study, if the patient agrees to participate.
- **3.** Simple 1:1 randomization of patients using the random system proposed in the protocol. The patient's CH should be noted for the group to which she belongs.
- **4.** Explanation of the procedure again on the day of the intervention, ensuring that it is not mentioned if anesthesia will be used to avoid bias in the evaluation of pain.
- **5.** Collection of the signed consent in consultation, before the intervention, to confirm participation

This procedure ensures that all ethical and legal regulations are complied with, and that the study is conducted in a controlled manner, with minimal risk of bias, ensuring data integrity and the well-being of participating patients.

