## Randomization process

Randomization will be carried out at the time the patient presents for the intervention (in consultation, when the indication is made), after she has read and signed the informed consent. At this time, you will be randomly assigned to one of two groups (under or without anesthesia) using the system previously described.

The inclusion of the patient's procedure in the trial will be recorded by writing the name in the Clinical Judgment along with the group to which she belongs according to the randomization process. The patient will also be given the specific document of inclusion in the trial to sign after explaining what it consists of

and give him consent for the test. The documents will be sent for consultation according to the usual channels after filling in the surgical demand register appropriately as it is standardized in the unit.

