## 3.1. Analysis by Protocol

Only those patients who complete the study after having reached the necessary sample size will be included.

Incomplete or non-compliant data will be excluded from the analysis.

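### The check of suitability for local anaesthesia is made after randomisation and in the anaesthesia arm only, so the two analysed groups may be selected by different rules

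*Protocol*

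**What the plan says.** **Timing of the draw.** Protocol, Randomization process: "Randomization will be carried out at the time the patient presents for the intervention (in consultation, when the indication is made"), and "after she has read and signed the informed consent". The Summary of the Consent Delivery Procedure gives the same order: randomisation is item 3, and item 4 is "Explanation of the procedure again on the day of the intervention".

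**Where the review sits.** The heading of Step 1 is "Application of Local Anesthesia (if applicable"). Within it, 3.1. Patient Preparation asks for a rapid review of the patient's "general condition will be carried out to confirm the suitability of local anesthesia". It gives no criteria and no consequence of failing.

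**The control step.** Under 2. Hysteroscopy, control patients have a preparatory step in which "the speculum will be placed to assess the vagina and cervix and the vagina and cervix will be irrigated with a syringe" with saline. No suitability review is mentioned.

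**Who is analysed.** Patients excluded from the study: if a patient is rejected after inclusion, "any data related to her will be removed from the clinical trial". Data Analysis, 3.1. Analysis by Protocol: "Incomplete or non-compliant data will be excluded from the analysis". No analysis of all randomised patients as allocated is stated.

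**Screening common to both arms.** Exclusion Criteria removes known allergy to local anaesthetics and general contraindications to hysteroscopy. The closing paragraph of Variables of post-procedure pain adds that history and allergies are collected to look for contraindications to the procedure.

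**The concern.** Randomisation makes the arms comparable only if whatever decides who is analysed afterwards works alike in both. Here one such decision can be taken in Group A alone. A Group A patient judged unsuitable would not receive her assigned treatment. The rules on rejected patients and non-compliant data then give a route by which her record leaves the comparison. A Group B patient in the same general condition does not face this check, and her record stays.

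The exclusions listed under Complex procedures also include events after the draw, but they are written for both arms. This check is differential by its position in the protocol. It is an uncriteried judgement by someone who knows the allocation, since Possible limitations states that the doctor giving the anaesthesia knows whether it is given. If general condition is related to reported pain, the mean VAS difference would partly reflect who was removed. The protocol itself names selection bias as a threat.

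**Working it through.** **Step 1. Does the review follow the draw?** Yes. The consent summary puts randomisation before the day of the intervention, and the review is part of the procedure-day steps. The sentence on timing under Randomization process could be read as same-day randomisation. Even then, Step 1 starts only once it is known to apply, so the arm is known before the review.

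**Step 2. Is it in one arm only?** Yes. It lies inside Step 1. The control step describes speculum and irrigation. Its comparison with giving the anaesthetic concerns how the irrigation is done and does not extend the review to controls.

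**Step 3. Is removal ordered or only possible?** Only possible. The review carries no stated consequence. The route out comes from two general rules elsewhere, on rejected patients and on non-compliant data.

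**Step 4. The plan's own sample size.** Inputs from Sample size calculation: difference 1.5, SD 2.0, 5% significance, 80% power. Two-sided testing is assumed, because H0 is equality of means.
- Standardised effect = 1.5 / 2.0 = 0.75.
- The exact two-sample t-test needs 28.9, hence 29 per group (58 in total), with power 80.1%. The stated figure is reproduced.

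**Step 5. Size of a one-arm removal.** Let f be the share of Group A removed and g the excess of their mean VAS over the mean m of the others. The documents give neither, so both are assumed.
- Group A mean with everyone kept: (1 - f) x m + f x (m + g) = m + f x g.
- Group A mean after removal: m. The shift is therefore f x g, with no matching shift in Group B.

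Type I error uses the normal approximation with n_A = 29 x (1 - f), n_B = 29, SE = 2.0 x sqrt(1/n_A + 1/n_B) and bias f x g.

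| f | n_A | shift for g = 1, 2, 3 | % of 1.5 | two-sided type I error |
|---|---|---|---|---|
| 2% | 28.4 | 0.02, 0.04, 0.06 | 1.3, 2.7, 4.0 | 0.050, 0.051, 0.052 |
| 5% | 27.5 | 0.05, 0.10, 0.15 | 3.3, 6.7, 10.0 | 0.051, 0.054, 0.059 |
| 10% | 26.1 | 0.10, 0.20, 0.30 | 6.7, 13.3, 20.0 | 0.054, 0.066, 0.086 |
| 15% | 24.6 | 0.15, 0.30, 0.45 | 10.0, 20.0, 30.0 | 0.059, 0.085, 0.130 |

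With g positive, the shift favours anaesthesia. With g negative, it runs the other way by the same amount. One patient is 1/29 = 3.4% of a group of 29.

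**Step 6. Power.** Final Estimate advises including 64 to 70 patients, or 32 to 35 per arm if split equally. With this as the only loss and an effect of 0.75, the t-test gives:
- 30 v 32: 82.7%
- 28 v 32: 81.3%
- 31 v 35: 85.0%

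**The case against.** **Removal is nowhere ordered.** A reader might infer that the plan directs unsuitable Group A patients to be withdrawn. It does not: the review has no failure outcome, and neither general rule mentions suitability. This stands, and the point is limited to what the rules permit.

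**Most unsuitable patients are already screened out.** Allergy and contraindications to the procedure are checked in both arms, and a last look before an injection is ordinary. This stands as to size: 2% or less of Group A, under one patient in 29, is plausible, and the effect is then negligible. It does not remove the asymmetry, because no criterion before the draw covers general suitability for local anaesthesia.

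**The bias need not favour anaesthesia.** A reader might infer that anxious or distressed patients would be the ones removed. The text speaks only of general condition, and anxiety is measured separately by STAI. A link with higher VAS is conjecture.

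**Power is not shown to suffer.** Taking patients from 29 per arm would suggest power below 80% (78.7% at 27 v 29, 77.0% at 25 v 29). That ignores the advised 64 to 70. Power falls below 80% only if other losses use up that allowance.

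**Unmasking is marginal.** A reader might add that a check in one arm reveals the allocation. Possible limitations already accepts that the patient is likely to notice the injections, so the check adds little.

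**It overlaps with the per-protocol analysis set.** Analysing everyone as allocated would remove this bias, so the two points are linked. They are not the same: that change alone leaves untreated patients in Group A, whereas moving the review before the draw largely avoids them.

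**Conclusion.** The point holds as a structural weakness. A judgement on suitability is made after randomisation, in one arm, by an operator who knows the arm, and the protocol's own rules allow a patient who fails it to disappear from that arm only.

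Its size cannot be fixed from the documents and is probably small. Under the assumed 2-15% removed with VAS 1-3 points higher, the Group A mean falls by 0.02-0.45 points (1-30% of the 1.5-point target), and two-sided type I error lies between 0.050 and 0.130. The upper ends need both assumptions at their extremes, and the sign depends on who is removed. No loss of power below 80% is claimed, and 29 per group is unaffected. The change is worth making because it is cheap and closes a selection route that cannot be corrected later if the records have been deleted.

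**What to change.** 1. In the selection criteria and Randomization process, make the same suitability review, with its clinical content unchanged, an eligibility step completed for every patient before the draw.
2. If a review is also made on the procedure day, make the same one in both arms at the same point, by adding it to the control step under 2. Hysteroscopy.
3. Amend Patients excluded from the study and 3.1. Analysis by Protocol so that a patient found unsuitable after randomisation stays in her allocated group for the primary comparison, with her VAS and the reason recorded.

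**Cost.** Protocol wording and a brief review in control patients; no change to the sample size. Item 3 dilutes the effect slightly: if a share f of Group A is untreated and gains nothing, the expected difference is 1.5 x (1 - f), so 1.47 at 2% and 1.275 at 15%. Item 1 should keep that share low. None of this sets a clinical rule on who is suitable.

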#### 3.2. Anesthesia Injection

- The uterosacral ligaments are identified through the posterior region of the cervix, on both sides. 2 vials (3.4 ml) of 3% Mepivacaine will be injected into each uterosacral ligament, using a 25 mm Carpule needle.
- The needle should be inserted approximately 2-3 mm deep at each injection site.
- Infiltration should be carried out slowly, to avoid rapid dispersion of the anesthetic and to ensure its appropriate local action.

#### 3.3. Post-Injection Monitoring

- At least 1 minute after injection should be allowed before starting hysteroscopy to ensure the effect of the anaesthetic.
- In case of persistent severe pain, additional measures may be considered, such as a new administration of anesthetic or complementary sedation, if indicated and approved.

## **Step 2: Entry by Vaginoscopy**

The procedure will be initiated by vaginoscopy, ensuring clear visual access to the intervention area.

The insertion of the hysteroscope into the cervical canal will be performed at least 1 minute after the application of the local anesthesia.

## **Step 3: Insertion into the Endocervical Canal**

The hysteroscope will be carefully inserted into the endocervical canal, using the minimum of maneuvers necessary to reduce the patient's discomfort.

